#### Aim 1c. Proportion of patients achieving clinically meaningful change.

We anticipate that the FIT Teens intervention will result in a greater proportion of patients achieving the binary outcome of clinically meaningful reduction in FDI compared to CBT and GAE. This difference is expected to be between 15%-20% based on our pilot study of FIT teens and our previous trial of CBT showing ~55% of the FIT group and 35-40% of CBT participants achieving clinically meaningful change. The proportion of GAE patients achieving this binary outcome is expected to be similar to CBT. Power was calculated via G\*Power3 assuming proper handling of missing data and n = 105 within the three arms available for analysis. Results showed power will be 0.79 for either the FIT vs. CBT or FIT vs. GAE comparison if difference between two independent proportions is at least 17% or greater (False Discovery Rate Type-1 error control will be used to evaluate results from both tests). A difference in proportion of  $\geq 17\%$  between FIT Teens and CBT or GAE will provide useful information for patients and providers about the relative efficacy of the interventions in achieving clinically meaningful improvement in functioning.

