Randomized clinical trial of CBT in adolescents with JFM. The main objective of this completed 4-site single-blind randomized clinical trial (R01AR050028, PI: [name]) was to test whether (CBT) was superior to fibromyalgia education (FE) in reducing functional disability in JFM. Participants were 114 adolescents (ages 12-17) with JFM. After being stabilized on usual medical care for 8 weeks, patients were randomized to either CBT or FE and received 8 weekly individual sessions with a therapist and 2 post-treatment booster sessions (at 2- and 4-months). Assessments were conducted at baseline, immediately following the 8-week treatment and at 6-months follow up. Retention was excellent (87.7% completing the trial per protocol) and there were no study-related adverse events. The results of this rigorously controlled RCT were that CBT was significantly superior to FE in reducing functional disability (95% CI 1.57-9.22; p = 0.007) with a large effect size for CBT (d = .85). CBT also resulted in a significant, but small reduction in pain (Mean reduction from 5.7 on a 0-10 scale to 4.9 at the end of treatment; d = .22)¹. This study demonstrated that CBT is a highly promising intervention for reducing disability in adolescents with JFM. However, although the effect size for functional disability improvement was large, a secondary analysis using the Reliable Change Index as a cut-off for clinical significance (reduction in FDI score by ≥ 7.8 points) showed that 60% of patients did not achieve *clinically meaningful* changes in disability. Pain reduction was also not sufficient to be considered clinically significant using a criterion of $\geq 30\%$ improvement². These findings highlighted *the need for more powerful interventions to achieve*

clinically meaningful improvements in disability and pain in JFM.

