Through an iterative process in Phase I testing, several changes were made to the FIT Teens protocol, namely, 1) later timing of sessions, i.e., after 4 pm to create less conflict with school times, 2) increasing the session length from 60 to 90 minutes to allow ample time for CBT and exercise components, more education and review of home practice 3) several modifications to exercises to allow a range of fitness abilities 4) adding illustrated handouts about how each of the exercises related to daily functional abilities 5) addition of a sleep hygiene component 6) providing written instructions to help them remember homework exercises and 7) specific instructions for gradually increasing engagement in moderate -vigorous activity of their choice outside of sessions to eventually build-up to 30 minutes of exercise at least 2 times per week by the end of treatment. Patients and parents also requested periodic booster sessions to help with maintenance and to extend group support for continued coping and engagement with the program. Of the 16 patients enrolled, 12 patients completed disability and pain measures before and after treatment. Mean FDI reduction after the 8-week intervention was over 10 points (24.75 to 14.25) which was equivalent to effects seen in our published CBT trial at the 6-month time point showing that these changes can be achieved much faster with the combined FIT Teens intervention. Moreover, 50% of the patients achieved a clinically significant reduction in disability (based on the Reliable Change Index defined \geq 7.8 point reduction) at post-treatment. Based on our knowledge of CBT effects from our completed trial, we expect that the reduction in disability will become even larger over follow-up (with periodic booster sessions). Pain reduction after treatment was small as expected (Mean VAS 6.63 to 6.05), due to ongoing adaptation to the new exercise regime, but continued to decline over time as patients adapted to higher (self-reported) activity levels (based on phone-call follow-up 3-5

months after treatment ended, the last FIT Teens group of 4 adolescents reported and average pain VAS of 4.75, a >30% reduction).

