Power was again calculated via the external Monte Carlo simulation capabilities in Mplus in two steps. First, 5000 dataset replications of hypothetical FDI scores were generated in a multiple group SEM format assuming: 1.) standardization of FDI scores, 2.) maintained differences between the three groups at 6-, 9-, & 12-months as follows: GAE (d = 0.40), CBT (d = 0.52), & FIT (d = 0.90), and 3.) N = 315 randomized(n = 105 per group) available for analysis assuming proper missing data handling. Second, the 5000 Monte Carlo replications were then analyzed using a longitudinal SEM assuming an intercept-only model (i.e., slope fixed and random effects both = 0) with dummy-coded CBT & GAE groups (FIT = reference). Results showed power ≥ 0.80 if the standardized 'intercept on group' coefficient for either CBT or GAE is $\beta > 0.38$ assuming proper handling of cluster by site nesting as described above.

Aim 1c. Proportion of patients achieving clinically meaningful change.

We anticipate that the FIT Teens intervention will result in a greater proportion of patients achieving the binary outcome of clinically meaningful reduction in FDI compared to CBT and GAE. This difference is expected to be between 15%-20% based on pilot studies showing ~55% of FIT and 35-40% of CBT groups achieving clinically meaningful change. The proportion of GAE patients achieving this binary outcome is expected to be similar to CBT. Power was calculated via G*Power3 assuming 20% attrition and proper handling of missing data making n = 105 within the three arms available for analysis. Results showed power will be ≥ 0.80 for either the FIT vs. CBT or FIT vs. GAE comparison if difference between two independent proportions is at least 17% or greater (False Discovery Rate Type-1 error control will be used to evaluate results from both tests). A difference in proportion of $\geq 17\%$ between FIT Teens and CBT or GAE will provide useful information for patients and providers about the relative efficacy of the interventions.

K. Data and Safety Monitoring Plan

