To test changes in the dichotomous (improved vs not improved) endpoints of functional disability from baseline to 3-month follow-up, baseline FDI scores will be subtracted from the 3-month follow-up FDI to identify those who did and did not achieve a clinically significant FDI change score. Results will be analyzed via separate difference between two independent proportions analyses for FIT vs. CBT & FIT vs. GAE testing  $H_0$ : 50% of participants in the three study arms will achieve a reliable FDI decrease versus  $H_A$ : 55% of participants in the FIT arm, and 35%-40% of participants in each of the CBT and GAE arms, will achieve a clinically significant FDI decrease.

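### The responder aim's power of 0.79 is stated at 17 points, but the SAP's 55% against the only documented CBT rate of 40% is 15 points (two-sided power about 0.59), and neither the 55% nor the 35% can be traced

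*SAP*

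**What the plan says.** Both documents plan to compare the proportion of patients whose FDI falls by at least 7.8 points at 3-month follow-up, FIT against CBT and FIT against GAE. The SAP lists this under its primary aims (H3a, H3b).

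- **SAP 4.0, Aim 1c**, expects a gap of 15 to 20 points and bases it on "our pilot study of FIT teens and our previous trial of CBT showing ~55% of the FIT group and 35-40% of CBT participants" reaching the criterion. GAE is expected to resemble CBT. Power is 0.79 for either comparison if the difference is 17 points or more, with 105 per arm available for analysis and false discovery rate control over the two tests.
- **Protocol 5.J, Aim 1c**, on the same gap: "based on pilot studies showing ~55% of FIT and 35-40% of CBT groups achieving clinically meaningful change". Here power is at least 0.80 for the same 17 points and the same 105 per arm.
- **SAP 6.3 (H3a/H3b)** puts the rates into the alternative hypothesis: "55% of participants in the FIT arm, and 35%-40% of participants in each of the CBT and GAE arms". Protocol 5.G does the same.
- **Protocol 2.B, FIT pilot:** "Of the 16 patients enrolled, 12 patients completed disability and pain measures before and after treatment"; at post-treatment "50% of the patients achieved a clinically significant reduction in disability", on the 7.8-point criterion.
- **Protocol 2.B, CBT trial:** the same criterion "showed that 60% of patients did not achieve" a clinically meaningful change, which leaves 40% responders. Protocol 2.A repeats the 60% as approximate.
- **SAP 6.0 and Protocol 5.C** set alpha at 0.05, two-sided, unless otherwise noted. No exception is noted for this aim.

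**The concern.** The rates are presented as results that earlier studies showed, yet the two documents name different studies and neither prints a 55% or a 35%. The only CBT responder rate in print is 40%, at the top of the 35-40% range. Set against the SAP's own 55%, it gives 15 points, the bottom of the expected range and below the 17 points at which power is stated.

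The single power figure therefore describes a case that the documented CBT rate does not reach. If H3a then comes out non-significant, a reader who trusts 0.79 may conclude that FIT adds nothing in clinically meaningful improvement, when the trial had little more than an even chance of detecting the lower end of its own expected range.

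**Working it through.** **Inputs.** n = 105 analysed per arm, 1:1 (SAP 4.0); alpha 0.05 two-sided (SAP 6.0); FIT 55%, comparator 35-40% (SAP 4.0 and 6.3); printed rates 50% and 40% (Protocol 2.B). Clustering is ignored at this step.

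**Formula.** Pooled two-proportion z-test, with p̄ the mean of p1 and p2:

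power = Φ{ [ |p1 − p2| − 1.96 √(2 p̄(1 − p̄)/n) ] / √( [p1(1 − p1) + p2(1 − p2)]/n ) }

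**The plan's own figure: 17 points, stated 0.79.** For 55% vs 38%, p̄ = 0.465. The critical difference is 1.96 × √(0.49755/105) = 0.1349, and the standard error under the alternative is √(0.4831/105) = 0.0678. Power = Φ[(0.17 − 0.1349)/0.0678] = Φ(0.517) = 0.70. Placing the 17 points elsewhere changes little: 0.696 for 57% vs 40% and 0.703 for 52% vs 35%. Other two-sided methods for 55% vs 38% give 0.71 (unpooled), 0.70 (arcsine), 0.65 (continuity-corrected) and 0.64 (Fisher exact). A one-sided 0.05 test gives 0.797 to 0.803, close to the stated figure, but both documents specify two-sided testing. What was entered in the software cannot be seen. Two-sided power of 0.78 at 17 points needs a comparator rate near 20%.

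**Across the plan's range.**

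| FIT vs comparator | Difference | Calculation | Two-sided power |
|---|---|---|---|
| 55% vs 40% | 15 points | Φ[(0.15 − 0.1351)/0.0681] | 0.59 |
| 55% vs 38% | 17 points | Φ[(0.17 − 0.1349)/0.0678] | 0.70 |
| 55% vs 35% | 20 points | Φ[(0.20 − 0.1346)/0.0673] | 0.83 |
| 50% vs 40% (printed rates) | 10 points | Φ[(0.10 − 0.1346)/0.0683] | 0.31 |

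Power of 0.80 needs about 19 points. With FIT at 55%, a 17-point difference needs a comparator rate of 38% or less.

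**False discovery rate control.** Under a Benjamini-Hochberg rule for two tests (assumed; the plan does not name the procedure), a comparison must reach 0.025 when the other is not significant. Power at 0.025 is 0.47, 0.59 and 0.75 for 15, 17 and 20 points. Cohort clustering would generally lower power further. The documents give no intraclass correlation, so that loss is not quantified here.

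**Tracing the rates.** The FIT pilot's 50% of 12 is 6 of 12, exact 95% CI 21% to 79%, so it cannot separate 50% from 55%. Protocol 2.B gives no responder rate for the second-site pilot (N=12) or the randomized FIT vs CBT pilot (N=40).

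**Compatibility with Aim 1a.** Assume an FDI SD of 10 and a baseline-to-3-month correlation of 0.5. The SD of change is then 10 × √(2 × 0.5) = 10. Mean reductions at d = 0.90, 0.52 and 0.40 are 9.0, 5.2 and 4.0 points. The proportion reaching 7.8 is Φ[(mean − 7.8)/10]: Φ(0.12) = 55% for FIT, Φ(−0.26) = 40% for CBT and Φ(−0.38) = 35% for GAE. That is 15 points against CBT and 20 against GAE.

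**The case against.** A reader might infer from the printed 50% and 40% that the plan's evidence supports about 10 points, not 15 to 20, and that the inputs were shifted in FIT's favour. The documents do not support that.

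- **Source.** Protocol 5.J refers to pilot studies in the plural. The randomized pilot had a group-CBT arm and 3-month follow-up, so the 55% may come from unprinted or pooled pilot results.
- **Time point.** The 50% is a post-treatment figure, and Protocol 2.B expects larger reductions later. The CBT trial had no 3-month visit, and the time point of its 40% is not stated. Subtracting one from the other does not estimate the 3-month contrast.
- **CBT input.** The 40% lies inside the stated 35-40%, so this input has not moved.
- **Other evidence.** The Aim 1a effect sizes convert to 15 and 20 points under the assumptions above. The randomized pilot's post-treatment gap is 23.9 − 18.7 = 5.2 FDI points. With equal baselines and an SD of change of 8 to 12 (assumed), the largest possible responder difference, 2Φ(5.2/(2 SD)) − 1, is 25 to 17 points. That is an upper bound from a small study (p = .07), but it does not point to 10.

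It can also be said that the power statement is conditional on 17 points, which the plan justifies as useful to patients and providers, not as a pilot finding. All of this stands. It does not rescue the stated figure: two-sided power at 17 points is about 0.70, and the plan's expected range begins at 15.

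**Conclusion.** The concern holds in a limited form. The 55% and 35% are not traceable in the documents, and the SAP and protocol disagree on where they come from. Taking the 55% as given, the documented CBT rate of 40% yields 15 points, where two-sided power is about 0.59 instead of the 0.79 stated at 17. Across the plan's own range it runs from 0.59 to 0.83, and it exceeds 0.80 only from about 19 points.

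These values assume 105 analysed per arm, independent patients and an unadjusted two-sided 0.05 test, so they are generally optimistic for the trial as designed. The 0.31 at 50% against 40% is a pessimistic scenario, not an estimate of the trial's power: a 10-point 3-month difference is not established. The sample size and the planned analysis are not put in question by this point.

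**What to change.** In SAP 4.0 Aim 1c and Protocol 5.J Aim 1c:

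1. Replace the single power figure (0.79 in the SAP, at least 0.80 in the protocol) with two-sided power across the plan's range: about 0.59 at 55% vs 40%, 0.70 at 55% vs 38% and 0.83 at 55% vs 35%. Say that these precede cohort clustering and false discovery rate control.
2. Add 50% vs 40% (about 0.31) as a pessimistic scenario, labelled as coming from post-treatment data on 12 FIT pilot completers and from the CBT trial.
3. Give one agreed source, denominator and time point for the 55% and the 35%, or call them planning assumptions.

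Do not put 50% vs 40% into the alternative hypothesis in SAP 6.3 or Protocol 5.G; a post-treatment rate from 12 patients is no better a basis for a 3-month hypothesis.

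The cost is wording in two documents and a less favourable stated power for H3. No more patients are needed.

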3. STUDY DESIGN

A. Overview

The project is a 3-arm multi-site randomized clinical trial which will examine the efficacy of the new FIT Teens intervention in reducing disability in adolescents with JFM compared to CBT only or GAE only. A longitudinal design will be employed with assessments at baseline, mid-treatment, post-treatment, 3-, 6-, 9- and 12-months follow-up. We will enroll up to 420 JFM patients ages 12-17 into this trial (with at least N=105 randomized to each condition). Each treatment arm will consist of 16 in-person group-based sessions (or remote group-based sessions administered via video-platform during pandemic restrictions) held twice per week over 8 weeks. Sessions last 90 minutes and will be led jointly by a psychologist/therapist and exercise trainer using manualized protocols. Group size will vary from 4-6 JFM patients per group which has been found to be the ideal group size in our pilot work based on feedback from both trainers and patients. Parents will be included in 6 of the 16 sessions and they will receive education about the treatment and instructed in how to support the teen in their behavior change efforts outside of sessions to enhance generalizability to the home environment. After the 8-week active treatment phase, participants will return for a total of 4 group-based "booster/ maintenance" sessions (according their group assignment), or attend booster sessions via remote video sessions, at 3 month intervals through the follow-up phase in order to review their use of skills/maintenance of exercise and encourage continued practice.

The primary study endpoint is the 3-month follow-up assessment. Additional follow-ups will be conducted at 6-, 9- and 12-months post-treatment. Participants randomized after 11/22/22 will not complete the 9- or 12- month follow up or the last 2 "booster/maintenance" sessions due to a reduction in the scope of work in this project to complete the project expeditiously within the remaining timeframe and funding support.

(Protocol continued on next page)

B. Study Visit Flowchart

Participants randomized after 11/22/22 will not complete the 9- or 12-month follow up assessment (T6 and T7) or the last 2 booster sessions due to a reduction in the scope of work in this project.

C. Participants

Inclusion Criteria

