Tests of the mechanisms that influence functional disability and pain intensity outcomes will be conducted using a multiple path mediation analyses. 1) All possible indirect pathways between psychological mechanisms (coping skills, decreased fear of activity, adherence) and physical assessments (biomechanics, physical activity and physical fitness) with the outcomes of functional disability and pain intensity will be tested for statistical significance within each of the three (FIT, CBT & GAE) groups via bias-corrected bootstrap testing of all indirect pathways, and 2) The magnitudes of the indirect effects will be tested for statistically significant differences between the three treatment groups via a multiple-group analysis. The False Discovery Rate will be used to maintain the nominal Type-1 error rate for all indirect effect tests.

J. Sample size and rationale (Power calculation)

The primary outcome for this RCT is reduction in functional disability. As such, the power calculations provided below are for the ability to detect whether FIT Teens results in significantly greater reduction in disability for Aims 1a, 1b and 1c.

Aim 1a. Differences between groups at the 3-month primary endpoint.

Power was calculated via the external Monte Carlo simulation capabilities in Mplus in two steps. First, 5000 dataset replications of hypothetical FDI scores were generated in a multiple group SEM format assuming: 1.) standardization of FDI scores, 2.) no differences in the three groups at baseline due to randomization (d = 0), 3.) group differences in FDI scores at 3 months, consistent with effect sizes from prior studies as follows: GAE (d = 0.40), CBT (d = 0.52), & FIT (d = 0.90), and 4.) N = 420 minus 20% attrition makes N = 336 (n = 112 per group) available for analysis assuming proper missing data handling. Second, the 5000 Monte Carlo replications were then analyzed using a longitudinal SEM assuming linear trend (i.e., slope loadings coded 0, 2, & 3) with dummy-coded CBT & GAE groups (FIT = reference). Results showed power ≥ 0.80 if the standardized 'slope on group' coefficient for either CBT or GAE is $\beta > 0.12$ assuming proper handling of cluster by site nesting as described above. With a revised sample size of N=315 (n=105 per group), our recalculated power analysis estimates power of >.80 for the GAE arm (versus reference group) and .79 for the CBT arm.

Aim 1b. Maintenance of treatment gains over follow-up.

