## 4.0 Power and Sample Size Estimates

(Note: the following power calculation is an amended version from the original power calculation and based on the R01 Ancillary Funded Award in February 2023 which reduced the scope of the RCT to accommodate delays due to the COVID19 pandemic)

The primary outcome for this RCT is reduction in functional disability. Power was determined for the ability to detect whether FIT Teens results in significantly greater reduction in FDI scores for Aims 1a, 1b, and 1c. Assumptions for power calculations were based on previous research showing statistically significant decreases in disability resulting from CBT (Cohen's d = .52) and GAE (Cohen's d = .40) interventions (6,7) and our pilot studies showing stronger post-treatment effect sizes for FIT Teens (d = .95 - 1.22). Power estimates were calculated with more conservative effect sizes for FIT Teens (i.e., d = .90). All power calculations were based on the assumption of 20% attrition and proper handling of missing data.

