## 5.0 Analysis Population

A total of 315 adolescents 12.0 to 18.0 years of age ( $n = \sim 105$  / group for 3 IV groups) will be needed for this study. The samples used for analysis are as follows:

- Sample 1. All JFM subjects with a diagnosis of fibromyalgia consistent with current American College of Rheumatology criteria, irrespective of intervention group (n = 315).
- Sample 2. All JFM subjects receiving the FIT Teens intervention (n = 105).
- Sample 3. All JFM subjects receiving the CBT treatment (n = 105).
- Sample 4. All JFM subjects receiving the GAE treatment (n = 105).

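### The stated Aim 1c power (0.79 in the SAP, at least 0.80 in the protocol) does not reproduce at two-sided 0.05; with 105 per arm and a 17-point difference it is about 0.70

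*SAP*

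**What the plan says.** The comparison is Aim 1c in the protocol and in SAP Section 4.0, and Aim 3 (H3a, H3b) in SAP Section 2.0, where it stands among the primary aims.

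- **Power.** The SAP gives "Results showed power will be 0.79 for either the FIT vs. CBT or FIT vs. GAE comparison if difference between two independent proportions" is 17 points or more. Protocol Section 5.J puts power at or above "0.80 for either the FIT vs. CBT or FIT vs. GAE comparison" for the same difference. Both use 105 per arm, name G*Power3, and expect about 55% responders on FIT and 35-40% on CBT, with GAE similar to CBT. Both say FDR control will be applied to the two tests.
- **Alpha.** Protocol Section 5.C and SAP Section 6.0 set 0.05 two-sided for all analyses unless otherwise noted. No Aim 1c text notes an exception.
- **Test.** Protocol Section 5.G and SAP Section 6.3 plan two separate comparisons of independent proportions, without naming the test statistic.
- **Attrition.** Protocol Section 5.J, Aim 1c, reaches its n by "assuming 20% attrition and proper handling of missing data making n = 105 within the three arms available for analysis". SAP Section 4.0 adds: "All power calculations were based on the assumption of 20% attrition and proper handling of missing data".
- **Numbers randomised.** Protocol Section 5.J, Aim 1b, has "N = 315 randomized(n = 105 per group) available for analysis". Protocol Section 3.A allows up to 420 enrolled, "with at least N=105 randomized to each condition". The SAP's Analysis Population section says "A total of 315 adolescents 12.0 to 18.0 years of age" will be needed. The first Aim 1a calculation in the protocol has "N = 420 minus 20% attrition makes N = 336 (n = 112 per group", before a revision to 315.

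**The concern.** The same n, difference and response rates carry two different power values. The gap between 0.79 and 0.80 is small and could be rounding. The larger difficulty is that a 17-point difference between proportions near one half, with about 100 per arm, should fall well short of 0.80 in a two-sided 5% test.

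The responder comparison carries the claim of clinically meaningful improvement, and the power text singles out 17 points as a difference that would be useful to patients and providers. If true power is well below the stated value, a non-significant result would be read as stronger evidence against such a difference than it is.

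The attrition wording raises a second doubt. If 105 is the number randomised, it cannot also be what is left after a 20% loss.

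**Working it through.** **Inputs.** n = 105 per arm; difference 0.17; FIT 0.55 against comparator 0.38, with 0.52 v 0.35 and 0.57 v 0.40 covering the stated 35-40%; alpha 0.05 two-sided (z = 1.960).

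**Formula (pooled z-test).** With p̄ the mean of the two proportions:

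- SE0 = √[2 p̄(1 − p̄)/n]
- SE1 = √[(p1(1 − p1) + p2(1 − p2))/n]
- power = Φ[(|p1 − p2| − z·SE0)/SE1]

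**Attempt to reproduce 0.79 or 0.80.** p̄ = 0.465. SE0 = √(0.49755/105) = 0.0688. SE1 = √(0.4831/105) = 0.0678. Then (0.17 − 1.960 × 0.0688)/0.0678 = 0.517, and Φ(0.517) = **0.697**. The other pairs 17 points apart give 0.703 (52% v 35%) and 0.696 (57% v 40%).

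**Other two-sided tests, 55% v 38%, n = 105:**

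| Test | Power |
|---|---|
| Unpooled z | 0.708 |
| Arcsine | 0.699 |
| Pooled z | 0.697 |
| z-test, exact enumeration | 0.685 |
| Fisher exact | 0.635 |

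In the pooled test, 17 points reaches about 0.79 only with a comparator rate near 20% or lower, or near 64% or higher.

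**Where the stated figure could come from.** A one-sided 0.05 test (z = 1.645) at n = 105 gives Φ(0.837) = 0.799. A two-sided test at n = 131 gives 0.791, and 105/0.8 = 131.25. Either would match; the documents establish neither.

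**What 0.80 requires.** At 17 points (55% v 38%), 133 per arm gives 0.797 and 134 gives 0.800. At 105 per arm, the difference must be 19.1 to 19.2 points.

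**Over the expected 15-20 points, n = 105.** 55% v 40%: 0.59. 55% v 35%: 0.83. Only the upper end reaches 0.80.

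**Attrition.** 420 × 0.8/3 = 112 per arm; 315 × 0.8/3 = 84. Neither is 105. With 84 per arm, SE0 = 0.0770, SE1 = 0.0758 and power = Φ(0.253) = 0.60.

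**FDR control.** The plan names no procedure, so Benjamini-Hochberg is an assumption. Two million simulated trials (z-test, shared FIT arm, true rates 55/38/38) give, per comparison:

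| n per arm | Unadjusted | Adjusted |
|---|---|---|
| 105 | 0.69 | 0.65 |
| 84 | 0.61 | 0.56 |

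The unadjusted values differ slightly from the formula (0.697 and 0.600) because the counts are discrete.

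**Clustering.** The documents give no intracluster correlation (ICC). Assume 0.01 to 0.10, groups of 4 to 6, and design effect 1 + (m − 1)·ICC, so 1.03 to 1.50. A test that allows for the clustering then has power 0.52 to 0.69 at n = 105.

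**The case against.** **No test is named, so 0.79 could belong to another one.** Every two-sided variant checked is at least 8 points short. A one-sided test fits, but the plan's alpha is two-sided; if that is the origin, the stated power describes a test the plan does not make.

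**The attrition charge may be too strict.** Protocol Section 3.A gives a range, and 131 randomised per arm (about 394 in all) falls inside it and would leave 105. This is fair for that section alone. It fails against the Aim 1b sentence, the revised 315 in Aim 1a and the SAP's Analysis Population section, which make 315 the randomised or required total.

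**Eighty-four per arm is a complete-case figure.** The plan is intention-to-treat with multiple imputation, so the effective information probably lies between 84 and 105. This stands: 0.60 is conditional on only 84 contributing data. It is not a lower bound either, since FDR control and clustering could reduce it further.

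**The clustering range belongs to a cluster-adjusted test.** This also stands. SAP Section 6.3 speaks generally of GEE, but its H3 text describes plain two-proportion comparisons. For an unadjusted test the same assumed ICCs give 0.66 to 0.69, and the main harm would be to the type I error rate. The central finding needs no ICC.

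**The consequence is limited.** The primary endpoint is FDI at 3 months and the sample size is settled. Agreed: the correction changes how the responder result is read, not how it is analysed.

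**Conclusion.** The concern holds. At two-sided 0.05 with the documents' own rates and all 105 per arm credited, power for 17 points is about 0.70 per comparison. That is 9 to 10 percentage points below the stated figures and means a miss rate of about 30%. The result rests on the pooled z-test and independent observations; the choice among the two-sided tests checked does not rescue the stated value.

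The attrition statements also conflict, and on the less favourable reading power is about 0.60 before FDR control and clustering. The power arithmetic examined here concerns Aim 1c only and says nothing against the simulated power for Aims 1a and 1b. The unresolved meaning of 105 does extend to those aims, because they use the same 315.

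This should be corrected, with high confidence. It bears on the stated power, not on the validity of the analysis.

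**What to change.** In Protocol Section 5.J and SAP Section 4.0, Aim 1c, replace the power sentence with:

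> With 105 analysed per arm, a two-sided pooled z-test of two proportions at alpha 0.05 and 55% vs 38%, power is about 0.70 per comparison before FDR control and clustering; 0.80 power requires a difference of about 19 points.

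If another two-sided test is intended for the analysis, name it and give its own figure. If an FDR-adjusted figure is added, name the procedure and give both values on one footing, for example 0.69 unadjusted and 0.65 with Benjamini-Hochberg by simulation.

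Reconcile the 20% attrition statements in both documents with 105 per arm (315 in total) being the number randomised. If only 84 per arm are expected to contribute data, state about 0.60 before FDR control and clustering, and do not call it a lower bound. The 17-point relevance threshold can stay.

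The cost is one power sentence and one attrition clause in each document. No endpoint, planned comparison or sample size changes; the stated power becomes less favourable.
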